gastric emptying, and degradation in the large bowel by commensal bacteria; thus, a monosaccharide such as mannitol, which passes freely across the healthy intestinal barrier, is often co-administered to 'normalise' lactulose measurements. Following administration of both lactulose and mannitol the fractional excretion of the sugars is expressed as a ratio where mannitol is the denominator. Lactulose and mannitol absorption occurs mainly in the proximal small intestine and is complete within approximately 5 hours of oral administration. This approach has been previously used successfully in patients with severe burn injury and intestinal permeability was found to correlate with episodes of sepsis [Doig, 1998].

In order to assess the permeability of the large bowel a third oligosaccharide, sucralose, will also form part of the sugar absorption test. This synthetic sweetener (marketed by Tate and Lyle as 'Splenda') is not subject to the same degradation by large bowel commensal flora as lactulose and is therefore a better measure of large bowel permeability than lactulose. Again, this has formed part of previously described studies aiming to measure intestinal permeability [Del Valle-Pinero, 2013].

Lactulose, mannitol and sucralose will be co-administered to both healthy participants and participants following thermal injury. In order to document accurately the time course of change in permeability, thermally injured participants will be asked to undergo the test on alternate days for 14 days (the intense monitoring phase) followed by two convalescent samples at day 28 and month 6 (thermal injury participants). In order to produce an accurate baseline measurement, healthy participants will be asked to undergo three measurements of intestinal permeability over approximately a two week period.

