1. SUMMARY OF KEY PROTOCOL INFORMATION

1.1. Changes to the Protocol Defined Statistical Analysis Plan

This study was terminated prior to the full sample size being achieved. As a result the initially planned sample size of 25 for the thermally injured subjects is greatly reduced to 3. Changes from the originally planned statistical analysis specified in the protocol (Dated:26SEP2017) are outlined in Table 1.

Table 1 Changes to Protocol Defined Analysis Plan

Pro	Protocol		Reporting & Analysis Plan				
Sta	tistical Analysis Plan		Statistical Analysis Plan		Rationale for Changes		
•	Co -Primary Objective 1: To determine the impact of thermal injury on the magnitude of small intestinal permeability change as soon as possible following injury compared to healthy participants.	•	Summary statistics for Lactulose/Mannitol (L/M) ratio at entry will be provided. No formal stats analysis for comparing the groups.	•	No stats analysis due to limited sample size.		
•	Exploratory objective 1: Comparison of Fractional excretion of sucralose of TI participants with Healthy participants at baseline	•	Only summary will be provided. No formal stats analysis for comparing the groups.	•	No stats analysis due to limited sample size.		
•	 Exploratory objective 3: Number of ventilator-free days, vasopressor-free days, hemofiltration-free days, episodes of confirmed infection and sepsis, surgical interventions Total length of hospital stay Calculate critical care and thermal injury severity scores 	•	None of the endpoints will be analysed for final reporting.		 Due to limited sample size, these endpoints will not be analysed. Where relevant, these will be described using data from the SIFTI2 CRF in CSR. 		
•	Exploratory objective 4: Change in urine protein: creatinine and urine albumin: creatinine ratios	•	This endpoint will not be analysed.	•	The reason for collecting these data was to inform a pharmacokinetic model. As development of the molecule has been terminated, this model is no longer required, moreover data collected are so limited that analysis is not possible.		
•	Exploratory objective 5: Changes in microbiome of acute and convalescent stool samples	•	This endpoint is not considered for final analysis.	•	Only one stool sample has been collected from a TI patient thus no meaningful comparison is possible.		

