4.2. Baseline Definitions

For efficacy and biomarker endpoints, the baseline value will be Day 1 for both the groups. In case of missing Day 1 assessment, baseline would be set to missing.

Parameter	 	Study Assessments Considered as Baseline							
	Screening [1]	Day 1 (Baseline)							
Efficacy Assessments									
L/M Ratio		X	Day 1 (Baseline)						
Fractional excretion of sucralose		X	Day 1 (Baseline)						
Biomarkers Assessments									
Markers of intestinal mucosal damage		X	Day 1 (Baseline)						
Bacterial markers of translocation		X	Day 1 (Baseline)						
Safety Assessments									
Vital Signs	Χ		Screening						
Laboratory Assessments									
Haematology	Χ		Screening						
Clinical Chemistry	Х		Screening						
Routine Urinalysis	Χ		Screening						
[1] Screening = 1-2 Wks Prior to Day 1 (Heal	[1] Screening = 1-2 Wks Prior to Day 1 (Healthy Participants).								

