4.2.1. Derivations and Handling of Missing Baseline Data

For untransformed data, change from baseline at each time point is expressed as a difference (value at time point – value at baseline).

Definition	Reporting Details					
Change from Baseline [1]	= Post-Baseline Visit Value – Baseline Value					
% Change from Baseline [1]	= 100 x [(Post-Baseline Visit Value – Baseline Value) / Baseline Value]					
[1] If the baseline value is missing the change from baseline derivations will also be missing						

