10.5. Appendix 5: Derived and Transformed Data

10.5.1. General

Multiple Measurements at One Analysis Time Point

- Mean of the measurements will be calculated and used in any derivation of summary statistics but if listed, all data will be presented.
- If there are two values within a time window the value closest to the target day for that window will be used. If values are the same distance from the target, then the mean will be taken.

Study Day

- Calculated as the number of days from First STM Dose Date:
 - Ref Date = Missing → Study Day = Missing
 - Ref Date < First STM Dose Date → Study Day = Ref Date First STM Dose Date
 - Ref Data ≥ First STM Dose Date → Study Day = Ref Date (First STM Dose Date) + 1

Age

Age = Screening date – Date of Birth
 Date of birth will be imputed based on the assumption that all subjects were born on the 30th June (30 Jun YYYY).

Baux score

Baux score: Age + % Total Body Surface Area (TBSA) burned

10.5.2. **Efficacy**

Fractional Excretion of Lactulose/Mannitol/Sucralose

Data is provided to S&P in the form of quantity of material in micrograms/litre, based on a sample of urine.

Fractional excretion (FE) of lactulose or mannitol or sucralose = (urine concentration (micrograms/litre) × total urine volume excreted in litre) / probe input (micrograms).

Where,

- Urine concentration is provided in the BIOMARKER dataset,
- Urine volumes excreted are provided in the BIOLINK dataset,
- Probe input refers to the total STM taken (as per Table 7.1 of the protocol-5g Lactulose, 2g Mannitol and 2g Sucralose)

Urine concentration in the BIOMARKER dataset will be provided at two timepoints per visit (0-5hr) and (0-24hr)

FE will be calculated for timepoints 0-5 and 0-24 hours for Lactulose, Mannitol and Sucralose.

For calculations of the 0-24 FE's, total urine volume will be based on the following:

Total urine=urine excreted 0-5 hrs + urine excreted 5-24 hours.

Note: If urine excreted 0-5 hrs is missing then total urine should be considered missing.

Note: 1g=1000000 micrograms

L/M ratio

L/M ratio = FE lactulose / FE mannitol

Healthy Participant – Average

• Average = Mean of all data available at all timepoint for each healthy participant.

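### SAP 10.5.2 loses the 0-5 h L/M ratio when a urine volume is unrecorded, although volume cancels out of that ratio (minor)

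*SAP*

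**What the plan says.** Protocol 3.2.2 defines the measure: "the fractional excretion of the sugars is expressed as a ratio where mannitol is the denominator". SAP 10.5.2 implements this as "L/M ratio = FE lactulose / FE mannitol", where each FE is the urine concentration times the urine volume, divided by the probe input. The probe inputs are constants, 5 g lactulose and 2 g mannitol.

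The two ingredients come from different files: "Urine concentration is provided in the BIOMARKER dataset", whereas "Urine volumes excreted are provided in the BIOLINK dataset". Concentrations are supplied for two windows per visit, 0-5 h and 0-24 h. The one explicit rule for an absent volume concerns the 0-24 h total: "Note: If urine excreted 0-5 hrs is missing then total urine should be considered missing".

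SAP 4.1 rules out imputation across visits. For Day 1, SAP 4.2 states: "In case of missing Day 1 assessment, baseline would be set to missing". SAP 4.2.1 adds: "If the baseline value is missing the change from baseline derivations will also be missing".

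L/M at entry and its change over time remain the primary endpoints after termination (SAP 1.2.2). They are summarised without formal analysis (SAP 6.1.4). SAP 1.1 records that "the initially planned sample size of 25 for the thermally injured subjects is greatly reduced to 3".

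**The concern.** A concentration pair can exist without a volume, because assay results and volumes are held in separate datasets. The SAP offers no route to L/M that avoids the FEs. In that situation both FEs are missing and L/M is missing with them, although the ratio never needed the volume. An assayed value of the co-primary variable would be discarded for want of an irrelevant input.

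At stake is the completeness of the L/M tables and individual plots. No test result depends on it. In a TI group of three, though, each value is a large share of what can be reported, and a Day 1 gap carries through to every later change value for that participant and window.

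**Working it through.** The plan states no figure to reproduce here, so the check is algebra on its own formulas. The documents give no concentrations; those below are illustrative assumptions.

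**Inputs from SAP 10.5.2.** Lactulose dose 5,000,000 µg, mannitol dose 2,000,000 µg, and one urine volume V (litres) shared by both sugars in a 0-5 h collection. C_lac and C_man are the two concentrations in µg/L.

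**0-5 h window.**

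- FE lactulose = C_lac × V / 5,000,000
- FE mannitol = C_man × V / 2,000,000
- L/M = (C_lac × V / 5,000,000) / (C_man × V / 2,000,000) = (2/5) × C_lac/C_man = 0.4 × C_lac/C_man

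V has gone. With assumed C_lac = 12,000 and C_man = 240,000:

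| V (L) | FE lactulose | FE mannitol | L/M |
|---|---|---|---|
| 0.2 | 0.00048 | 0.024 | 0.020 |
| 0.6 | 0.00144 | 0.072 | 0.020 |
| 2.0 | 0.0048 | 0.24 | 0.020 |
| not recorded | missing | missing | SAP route: missing; direct route: 0.4 × 12,000/240,000 = 0.020 |

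**0-24 h window.** If the assayed sample is the physical pool of all urine from both collections, one concentration pair and one total volume apply, and the same cancellation holds. If the 0-24 h figure is instead rebuilt from separate fractions, the volumes act as weights. Take assumed 5-24 h concentrations of 6,000 (lactulose) and 40,000 (mannitol), with V1 and V2 the 0-5 h and 5-24 h volumes:

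L/M = 0.4 × (12,000 V1 + 6,000 V2) / (240,000 V1 + 40,000 V2)

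- V1 = 0.2, V2 = 1.8: 0.4 × 13,200/120,000 = 0.044
- V1 = 0.5, V2 = 1.5: 0.4 × 15,000/180,000 = 0.033
- V1 = 1.0, V2 = 1.0: 0.4 × 18,000/280,000 = 0.026

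The volumes are then needed. Protocol 9.8 leaves the measurement method to the SRM, so the documents do not settle which case applies.

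**Consequence of one unrecorded TI Day 1 0-5 h volume.**

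- Table 2.1 loses 1 of 3 entry values for that window. At the same SD, the standard error goes from SD/√3 = 0.58 SD to SD/√2 = 0.71 SD, a factor of √(3/2) = 1.22.
- Tables 2.2 and 2.3 lose all of that participant's values for the window, and Figure 2.3 loses 1 of at most 3 lines.
- Under the SAP's note on total urine, the 0-24 h total for that visit is also set to missing, so the 0-24 h L/M goes as well. Whether that second loss is avoidable depends on the SRM.

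**The case against.** The SAP follows the protocol's definition faithfully, and where a volume exists no reported value is wrong. That stands: the gap is an absent fallback, and the ratio itself is correctly defined.

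The trigger is hypothetical. Separate datasets make a mismatch possible but do not show that one occurred. For TI participants the protocol points the other way. Catheterisation on admission is described as standard at 15% TBSA or more (9.10.3), fluid balance is recorded every 24 hours (9.5.1), and accurate total volume is called critical (9.8). This lowers the likelihood but does not exclude a missing 0-5 h volume.

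An unrecorded volume may also signal a poorly measured collection. If concentrations drift within the window, L/M depends on which urine was kept, so a rescued value could be biased in a summary of three. Leaving it missing is a defensible conservative choice. This is the real downside, and it is why rescued values need a flag and a display with and without them.

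A reader might infer that the recording of collection times in Protocol 3.3.1 lets coverage be verified for every rescued sample. It does not support that. The entry is about 24-hour collections in ambulant uncatheterised patients and healthy participants, so it cannot be relied on for catheterised TI participants.

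Finally, the Day 1 knock-on comes from the baseline rule, which applies whatever the cause of the gap. Listing 24 may also show the concentrations, letting a reader work out the ratio by hand; its layout was not available to check.

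**Conclusion.** The point holds for the 0-5 h window as a minor robustness improvement. The cancellation is exact, given one shared volume and the fixed 5 g and 2 g doses. The loss follows from the only derivation given together with the no-imputation rule; no sentence in the SAP states it outright for 0-5 h.

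The size is conditional. One Day 1 gap in the TI group costs 1 of 3 entry values and that participant's change values for the window. The number of missing volumes is not stated and may be zero.

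Two stronger readings are tempting. One is that co-primary data have actually been lost; nothing in the documents shows a missing volume. The other is that volume is equally unnecessary at 0-24 h; that is true only if the assayed sample is the physical pool, which rests on the SRM. The SAP displays both windows and does not say which is primary. With summaries only, no inference changes.

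**What to change.** In SAP 10.5.2:

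- Compute 0-5 h L/M = (lactulose concentration / 5) / (mannitol concentration / 2) whenever both concentrations come from the same 0-5 h sample and the collection is not documented as incomplete.
- Require a volume only for the individual FEs. Sucralose FE still needs one.
- Flag L/M values derived without a volume in Listing 24, and present the L/M summaries with and without them.
- For 0-24 h, keep the existing missing rule unless the SRM confirms that the assayed sample is the physical pool of both collections.

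The cost is a few lines of SAP text and derivation code, one listing flag, and a repeat of the affected summaries if any value is flagged. Where a volume exists the result is identical to the current one, and the protocol's definition of the ratio is unchanged. The residual risk is admitting a value from a poorly measured collection, which the flag and the paired display make visible.

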10.5.3. Safety

Laboratory Parameters

- If a laboratory value which is expected to have a numeric value for summary purposes, has a non-detectable level reported in the database, where the numeric value is missing, but typically a character value starting with '<x' or '>x' (or indicated as less than x or greater than x in the comment field) is present, the number of significant digits in the observed values will be used to determine how much to add or subtract in order to impute the corresponding numeric value.
 - Example 1: 2 Decimal Points = '< x' becomes x 0.01
 - Example 2: 1 Decimal Point = '> x' becomes x + 0.1
 - Example 3: 0 Decimal Points = '< x' becomes x 1

10.6. Appendix 6: Reporting Standards for Missing Data

10.6.1. Premature Withdrawals

Element	Reporting Detail
General	 Subject study completion (i.e. as specified in the protocol) was defined as if he/she receives all planned doses of STM and completes the Day 15 in case of healthy participants and 6 months in case of participants with thermal injuries. Withdrawn subjects may be replaced in the study. All available data from participants who were withdrawn from the study will be listed and all available planned data will be included in summary tables and figures, unless otherwise specified.

10.6.2. Handling of Missing Data

Element	Reporting Detail		
General	 Missing data occurs when any requested data is not provided, leading to blank fields on the collection instrument: These data will be indicated by the use of a "blank" in subject listing displays. Unless all data for a specific visit are missing in which case the data is excluded from the table. Answers such as "Not applicable" and "Not evaluable" are not considered to be missing data and should be displayed as such. 		

10.6.2.1. Handling of Missing and Partial Dates

Element	Reporting Detail		
General	Partial dates will be displayed as captured in subject listing displays.		
Adverse Events	 The eCRF allows for the possibility of partial dates (i.e., only month and year) to be recorded for AE start and end dates; that is, the day of the month may be missing. In such a case, the following conventions will be applied for calculating the time to onset and the duration of the event: Missing Start Day: First of the month will be used unless this is before the start date of STM; in this case the STM start date will be used. Missing Stop Day: Last day of the month will be used, unless this is after the stop date of STM; in this case the STM stop date will be used. Completely missing start or end dates will remain missing, with no imputation applied. 		
	Consequently, time to onset and duration of such events will be missing.		
Concomitant Medications/ Medical History	 Partial dates for any concomitant medications recorded in the CRF will be imputed using the following convention: If the partial date is a start date, a '01' will be used for the day and 'Jan' will be used for the month If the partial date is a stop date, a '28/29/30/31' will be used for the day (dependent on the month and year) and 'Dec' will be used for the month. 		
	The recorded partial date will be displayed in listings.		

10.7. Appendix 7: Abbreviations & Trade Marks

10.7.1. Abbreviations

Abbreviation	Description
ACR	Albumin/creatinine ratio
ADaM	Analysis Data Model
AE/SAE	Adverse Event/ Serious Adverse Event
Anti-HBc	Anti-Hepatitis C
ART	Anti-retroviral treatment
CDISC	Clinical Data Interchange Standards Consortium
CFB	Change from Baseline
CFR	Code of Federal Regulations
CSR	Clinical Study Report
CV	Coefficient of Variation
DP	Decimal Places
eCRF	Electronic Case Record Form
FDA	Food and Drug Administration
GCP	Good Clinical Practice
GCSP	Global Clinical Safety and Pharmacovigilance
Gl	Gastrointestinal
GSK	GlaxoSmithKline
НВ	Hepatitis B
HBs AG	Hepatitis B Antigen
HCV	Hepatitis C
HIV	Human Immunodeficiency Virus
ICF	Informed Consent Form
ICH	International Conference on Harmonization
ICU	Intensive Care Unit
IEC	Independent Ethics Committee
IRB	Institutional Review Board
ISS	Investigator Sponsored Study
L/M	Lactulose/mannitol ratio
MODS	Multi-organ dysfunction syndrome
NC	Nominated Consultee
NIMP	Non-investigational medicinal product
PC	Personal Consultee
PCR	Polymerase Chain Reaction
PDMP	Protocol Deviation Management Plan
RAP	Reporting and Analysis Plan
SAC	Statistical Analysis Complete
SAE	Serious Adverse Event
SIFTI-2	A Multi-centre, Prospective Study to Examine the Relationship between Neutrophil Function and Sepsis in Adults and Children with Severe Thermal Injuries
SoA	Schedule of Activities
SRM	Study Reference Manual
STM	Sugar Test Material
TBSA	Total Body Surface Area
TI	Thermally Injured
TNF	Tumour Necrosis Factor
WOCBP	Women of Child Bearing Potential

10.7.2. Trademarks

Trademarks of the GlaxoSmithKline
Group of Companies

NONE

Trademarks not owned by the GlaxoSmithKline Group of Companies

SAS

10.8. Appendix 8: List of Data Displays

10.8.1. Data Display Numbering

The following numbering will be applied for RAP generated displays:

Section	Tables	Figures	
Study Population	1.1 to 1.8	N/A	
Efficacy	2.1 to 2.6	2.1 to 2.8	
Safety	3.1 to 3.4	N/A	
Biomarker	4.1 to 4.6	4.1 to 4.4	
Section	List	ings	
ICH Listings	1 to	23	
Other Listings	24 to 27		

10.8.2. Mock Example Shell Referencing

Non IDSL specifications will be referenced as indicated and if required example mock-up displays provided in Appendix 9: Example Mock Shells for Data Displays.

Section	Figure	Table	Listing
Efficacy	EFF_Fn	EFF_Tn	EFF_Ln
Safety	SAFE_Fn	SAFE_Tn	SAFE_Ln
Pharmacodynamic and / or Biomarker	PD_Fn	PD_Tn	PD_Ln

NOTES:

Non-Standard displays are indicated in the 'IDSL / Example Shell' or 'Programming Notes' column as '[Non-Standard] + Reference.'

10.8.3. Deliverables

Delivery [Priority] [1]	Description
SAC	Final Statistical Analysis Complete

NOTES:

1. Indicates priority (i.e. order) in which displays will be generated for the reporting effort

10.8.4. Study Population Tables

Study P	Study Population Tables					
No.	Population	IDSL / Example Shell	Title	Programming Notes	Deliverable	
Subject	Disposition					
1.1.	Evaluable	ES8	Subject Status and Reasons for Study Withdrawal	ICH E3, FDAAA, EudraCT. Include study group instead of treatment group.	SAC	
1.2.	Screened	ES6	Summary of Screening Status and Reasons for Screen Failure	Journal Requirements	SAC	
Protoco	l Deviation					
1.3.	Screened	DV1	Summary of Important Protocol Deviations	ICH E3. Include study group instead of treatment group.	SAC	
Populat	ion Analysed					
1.4.	Screened	SP1	Summary of Study Populations	IDSL. Include study group instead of treatment group.	SAC	
Demog	raphic and Basel	ine Characteristics				
1.5.	Evaluable	DM1	Summary of Demographic Characteristics	ICH E3, FDAAA, EudraCT Add %surface area burnt, Baux score and Body mass index. Include study group instead of treatment group.	SAC	
1.6.	Evaluable	DM11	Summary of Age Ranges	EudraCT Note: Include Age categories: Adult (18 – 64 years), >=65 – 84 years and >=85 years. Include study group instead of treatment group.	SAC	
1.7.	Evaluable	DM5	Summary of Race and Racial Combinations	ICH E3, FDA, FDAAA, EudraCT Include study group instead of treatment group.	SAC	

Study Po	Study Population Tables						
No.	No. Population IDSL / Example Shell Title Programming Notes						
Medical	Medical History						
1.8.	Evaluable	MH4	Summary of Medical Conditions	ICH E3 Include study group instead of treatment group. Add the medical status (Past/Current).	SAC		

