The lactulose-to-mannitol ratio is traditionally used to assess small intestinal permeability and sucralose to assess colonic permeability. Lactulose, mannitol and sucralose [henceforth referred to as sugar test material (STM)] will be intermittently administered enterally for the purpose of intestinal permeability measurement to examine permeability at different points along the GI tract and is described in Section 7. It is important to note that the administration of the STM is not therapeutic (lactulose and mannitol can be used as laxatives, however the amount in the STM is sub-therapeutic) and as such should be regarded as a non-investigational medicinal product (NIMP) [[Guidance Documents Applying Investigational Medicinal Products \(NIMPS\)](#), 2011].

An internal preliminary data review will be conducted. This review is described in Section 5.4.4.

Number of Participants:

Table 1 in Section 5.2 described the number of participants proposed for the study. Sample size is based on feasibility. No formal calculation of power or sample size has been performed, but a sample size of 15 healthy participants and 25 thermal injury participants ($\geq 15\%$ TBSA) should be sufficient to provide useful estimates of variability in lactulose:mannitol ratios, and any change in L/M ratio over time.

Treatment Groups and Duration:**Group 1: Healthy Participants**

The total duration of this study for healthy participants will be approximately two weeks, in addition to the screening window:

- Screening: up to 28 days before Day 1
- Day 1: study start and assessments will be performed
- Day 8 and Day 15

Group 2: Thermally injured participants

Thermal injury participants will be asked to participate for a total of 6 months (plus or minus 14 days).

- There will be no screening period. Thermal injury participants will be recruited within 24 hours of their admission to the burns unit at the study site.
- Intense monitoring phase: Assessments will be performed on alternate days for the first 14 days following study enrolment. If the participant is discharged prior to 14 days, the intense monitoring phase will end, but the participant will remain enrolled in the study.
- Convalescent monitoring phase: Assessments at 28 days and 6 months will be made on an outpatient basis if the participant has already been discharged from hospital.

Exception to monitoring periods:

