6.5. Exclusion Criteria for Thermal Injury Participants (Group 2)

Thermal injury participants are excluded from the study if any of the following criteria apply:

Medical Conditions

1. Chemical or electrical burn.
2. Multiple traumatic injuries with an Injury Severity Score (ISS) ≥ 16 (note: excludes burn in score system).

Prior/Concomitant Therapy

3. Patient received substantial undocumented management prior to arrival at the study site (burn centre) e.g. from paramedics or in a local accident and emergency department.
4. Systemic corticosteroid use.
5. Intravenous (IV) mannitol use.

Prior/Concurrent Conditions

6. Human immunodeficiency virus (HIV) infection.
7. Viral Hepatitis B or C infection.
8. Gastrointestinal disease (e.g. inflammatory bowel disease) which may affect intestinal permeability.
9. Previous bowel resection (e.g. hemicolectomy, small bowel resection)
10. Galatosaemia or severe lactose intolerance.
11. Bowel obstruction.
12. Renal dysfunction requiring renal replacement therapy (i.e. end-stage renal failure prior to thermal injury).
13. Active autoimmune disease and receiving immunomodulatory therapy e.g. rheumatoid arthritis anti-TNF.
14. Active chemotherapy for cancers or immunoremittive therapies (prednisolone, adalimumab) within 60 days of thermal injury.
15. Premorbid conditions of malignancy currently under treatment.
16. Previous bilateral lower extremity amputation.

NOTE: Due to the rapid recruitment period (within 24 hours of admission) for thermally injured participants, HIV and viral Hepatitis test results may not be available at the time of enrolment. In the event these tests return positive, the participant will be informed of the result(s) and withdrawn from the study (see Section 8.2.1). In the event that the participant has been recruited who lacked mental capacity to consent, the reason for their withdrawal (the positive HIV and/or viral Hepatitis test results) must not be shared with a personal consultee. According to UK law and the guidance of the British HIV association, if the participant's physician believes there is an overriding public interest to disclose the participant's results to a personal consultee who is a current or former sexual partner, then the result(s) may be disclosed without the participant's consent. This must be as a last resort. If the participant regains capacity, he/she will be informed of the positive test result(s).

Diagnostic assessments

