8. DISCONTINUATION CRITERIA

8.1. Discontinuation of STM administration

Discontinuation of STM administration can be considered by the investigator in the event that an adverse event to the STM is observed. Withdrawal of further STM administration does not require withdrawal from the study.

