3. ANALYSIS POPULATIONS

Population	Definition / Criteria	Analyses Evaluated
Screened	All participants who were screened for eligibility	Study PopulationAll Listings
Safety	Comprise of all participants who receive at least one dose of STM and have at least one post-dose safety assessment.	Safety
Evaluable	Comprises of all participants in the safety population excluding any healthy volunteers that received any concomitant medication or food and drink containing STM (lactulose, mannitol and sucralose), as identified by review of the protocol deviations.	EfficacyBiomarkerStudy Population

NOTES:

 Please refer to Appendix 8: List of Data Displays which details the population to be used for each display being generated.

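### SAP Table 1.1, the only withdrawal summary, runs on the Evaluable population, and SAP 10.6.1 credits the protocol with an all-doses completion rule that it does not contain

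*SAP*

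**What the plan says.** **Population.** In SAP 10.8.4, Table 1.1 is titled "Subject Status and Reasons for Study Withdrawal" and its population is Evaluable. The programming note ties it to ICH E3, FDAAA and EudraCT reporting. The neighbouring Tables 1.2 (screening status), 1.3 (important deviations) and 1.4 (population counts) run on Screened.

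SAP section 3 defines the two populations that matter:
- Safety: "Comprise of all participants who receive at least one dose of STM and have at least one post-dose safety assessment".
- Evaluable: "Comprises of all participants in the safety population excluding any healthy volunteers that received any concomitant medication or food and drink containing STM".

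**Completion.** SAP 10.6.1 says that completion, as the protocol specifies it, "was defined as if he/she receives all planned doses of STM and completes the Day 15 in case of healthy participants and 6 months" for thermal injury participants.

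**Protocol (Amendment 2).** Section 5.3 gives the study durations, the handling of early withdrawals and the end-of-study date. It sets no dosing condition for completion. Section 8.1 says: "Withdrawal of further STM administration does not require withdrawal from the study". For a thermal injury participant discharged before Day 14, the Synopsis says "the intense monitoring phase will end, but the participant will remain enrolled in the study".

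**The concern.** A disposition table should account for everyone who entered the study. Table 1.1 instead counts only people who were dosed, were assessed afterwards and, if healthy, avoided test sugars from other sources. A reader uses this table to judge whether the participants who remain are a selected group, so conditioning it on having been dosed works against its purpose.

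The protocol foresees early losses. Section 6.5 notes for thermal injury participants that "HIV and viral Hepatitis test results may not be available at the time of enrolment" and requires withdrawal if they return positive. Section 6.1.3 withdraws participants who regain capacity and decline consent. Healthy participants take STM at home the day before the visit, so one who doses and never attends may have no post-dose assessment. Sections 5.2 and 8.2.1 allow replacements, so a full-looking denominator would not reveal a loss.

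The completion rule raises a second problem. A healthy participant who stops STM but attends Day 15 has not left the study under Protocol 8.1, yet is not a completer under SAP 10.6.1.

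**Working it through.** The plan states no disposition figure, so there is nothing to reproduce. The check traces the definitions and then shows how much one participant moves a percentage.

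**1. Who is missing from Table 1.1.** Table 1.1 uses Evaluable, and Evaluable is a subset of Safety. Two groups fall out:
- (a) participants who entered but had no STM dose or no post-dose safety assessment;
- (b) healthy volunteers excluded for test-sugar intake, whether they withdrew or finished.

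**2. Who stays.** A participant withdrawn after one dose and one safety assessment is in Evaluable unless excluded under (b). The schedule of activities places the first test on Day 1, or Day 2 as the fallback, with adverse event review from the first dose. Most withdrawals for a late virology result or declined consent would therefore still be counted.

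**3. Where the missing people can be found.** Listing 2 (withdrawal reasons), Listing 3 (STM discontinuation) and Listing 7 (exclusions from populations) run on Screened. Table 1.4 counts population membership but gives no reasons. SAP 10.4.2 sends subject-level listings to the modular appendices. For groups (a) and (b), the withdrawal reason is therefore in no summary table.

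**4. Completion rule.** SAP 10.6.1 requires all planned doses and the final visit, and cites the protocol. Protocol 5.3 has no dosing condition, and Protocol 8.1 treats stopping STM and leaving the study as different events. SAP 1.3 says the study ended before any subject reached Day 28. Thermal injury completers at 6 months are therefore 0 with or without the dosing condition, and only healthy participants can be reclassified.

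**5. Size, for illustration.** Inputs: 15 healthy participants (planned, Protocol 10.2) and 3 thermal injury participants (SAP 1.1). The withdrawal counts below are assumptions, because the documents give none.

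| Assumed event | Table 1.1 as planned | On all enrolled |
|---|---|---|
| 1 of 15 healthy leaves before a dose or assessment | 0/14 = 0% | 1/15 = 6.7% |
| 2 of 15 healthy leave this way | 0/13 = 0% | 2/15 = 13.3% |
| 1 of 3 thermal injury leaves before dosing | 0/2 = 0% | 1/3 = 33.3% |
| 1 of 15 healthy finishes but is excluded for sugar intake; another withdraws after dosing | 1/14 = 7.1% | 1/15 = 6.7% |

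The last row shows that the error need not always lower the withdrawal percentage.

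Completion, if 1, 2 or 3 of 15 healthy participants stop STM but attend Day 15:
- with the dosing condition: 14/15 = 93.3%, 13/15 = 86.7% or 12/15 = 80.0%;
- without it: 15/15 = 100%.

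**The case against.** The best defence is that no information is lost. Listings 2, 3 and 7 cover all screened participants, Table 1.4 gives population counts by group, and SAP 10.6.1 itself promises to list all data from withdrawn participants. With 3 thermal injury participants, anyone reading Listing 2 sees every withdrawal and its reason. Reporting is descriptive throughout, and sponsor termination dominates thermal injury non-completion. All of this stands, and it keeps the point small. It does not make the table right: Table 1.1 is the display marked for formal reporting, and the listings sit outside the report body.

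Some stronger readings are tempting, but the documents do not support them:
- *Early withdrawals disappear.* Only groups (a) and (b) leave the table, and Listing 2 still shows their reasons.
- *Late virology or declined-consent withdrawals go uncounted.* Most would already have been dosed and assessed, so they remain.
- *Undosed participants withdrawn on a late result are certainly not screen failures.* Protocol 6.7 turns on being entered into the study but ties entry to no event. Section 6.5 does speak of withdrawal after enrolment, which points towards withdrawal without settling it.
- *A thermal injury participant discharged early who attends every later visit is misclassified.* That cannot arise in the data reported here, because nobody reached Day 28.
- *The withdrawal rate is understated.* No affected participant is documented, and group (b) can push the percentage the other way.

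Finally, the ES8 shell behind Table 1.1 is not shown. That the table applies the 10.6.1 definition is an inference.

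**Conclusion.** The point holds, with minor severity. Followed as written, SAP 10.8.4 leaves two identifiable groups out of the only withdrawal summary. SAP 10.6.1 also states a completion rule that the protocol does not contain and that conflicts with Protocol 8.1. The population error can affect either study group; the completion error can now affect only healthy participants.

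Its actual size is unknown. Each affected healthy participant is worth 6.7 percentage points if 15 enrolled, and one undosed thermal injury withdrawal among 3 would turn 1/3 into 0/2. These figures assume that the planned healthy number was reached, that 3 is the enrolled thermal injury count, and that such participants exist. The completion effect further assumes that Table 1.1 uses the 10.6.1 definition. The lactulose/mannitol and sucralose summaries do not depend on either rule.

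**What to change.** In the SAP:

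1. Run Table 1.1 on all enrolled participants (Screened minus screen failures), by study group, with a row for those withdrawn before the first STM dose. State how an undosed participant with a late positive virology result is classed, so that each person falls in either Table 1.1 or Table 1.2.
2. In 10.6.1, define study completion as attending the final scheduled visit. Remove the all-doses condition and its attribution to the protocol.
3. Report STM discontinuation as a separate line; Listing 3 already draws on these data.

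The cost is one population label, one definition and two table rows. No new data are needed and no other display changes.
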